### 10.6.1 ENROLLMENT/ RANDOMIZATION/ MASKING PROCEDURES

The randomization schedules will be developed prior to the enrollment of the first subject. There will be one schedule for Fitzpatrick types I-II and a second schedule for Fitzpatrick types III and higher. The randomization schedule is a simple list of assignments to the groups 'Treatment,' meaning that the subject will be given the Shade device and mobile application and 'Control,' meaning that the subjects will be given only the standard of care counseling to avoid UV. The following sequence of events at enrollment will ensure that the treating physician will be blinded to the subject assignment:

- (1) visit with study coordinator for screening, informed consent, and medical history.

If the subject passes screening and grants consent

- (2) physician visit.

During the physician visit, the study coordinator will take the next randomization from the randomization schedule. This schedule will be prepared by the sponsor in such a manner that the coordinator remains blind to the next assignment until it is requested. The sponsor has latitude to implement this using any reasonable physical or computational system. The subject assignment will be entered on the randomization schedule available only to the study coordinator and the study monitor.

- (3) wrap up conversation with study coordinator.

After the physician visit the study coordinator will sit with the subject in a separate room. The next visit or visits will be tentatively scheduled. If the subject is in the treatment group, the device will be provided and either the coordinator or a sponsor representative will work with the subject to setup the mobile application and ensure that subject understands how to use the device.

At subsequent visits subjects in the treatment group will be instructed to

- (1) avoid discussing their assignment with the physician.
- (2) place the shade sensor in a purse or pocket out of view of the physician
- (3) mention to the study coordinator if the subject of the assignment came up in conversation with the physician.

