## 4 STUDY DESIGN AND ENDPOINTS

### 4.1 DESCRIPTION OF THE STUDY DESIGN

This randomized partially blinded study will recruit 120 patients with a history of actinic keratosis (AK) lesions. A control versus study group analysis will be performed where 50% of the subjects will be randomly assigned (balanced by Fitzpatrick skin type, separate randomization lists will be made for type I&II and types III-VI, at time of first visit subjects will be assigned to study or control group by giving them the next assignment on the appropriate list) to use the SHADE sensor and its app (study group), while the other 50% (control group) will receive standard of care UV counseling(placebo). Subjects will have 3 visits. The first and last visit will be standard of care visits at 0 month (enrollment), and the conclusion of their involvement. The second visit will be scheduled 3 months after the enrollment visit. The final visit will be scheduled as soon as practical, but at least 3 months after visit 2 and after September 30. On arrival at each visit, study personnel will pre-screen patients to ensure that the sensor is not visible to physician prior to examination, for example by placing it in their pocket. At each follow up visit, the number of actinic keratosis on the face and hands will be counted and photographed. They will be treated as per standard of care protocol with cryotherapy or curettage. General use of field therapies will not be permitted during the trial. Any lesions suspicious of non-melanoma or melanoma skin cancer will be photographed and biopsied as part of the standard of care algorithm. Cyclobutane pyrimidine dimers (CPD) levels will be measured by ELISA from exposed (cheek) and unexposed (buccal mucosa) skin scrapings collected at the first and last visit. For each patient, the CPD level from exposed skin will be normalized to the sun protected CPD level measured from unexposed skin. We will compare the normalized CPD level of control versus study participants at each timepoint and their average CPD change over time.

We will then compare these levels with Shade UV measurements. Finally, patients will also answer questions in PROMIS (Patient-Reported Outcomes Measurement Information System) in the fields of anxiety, depression and ability to participate socially to gauge their attitudes toward the sensor

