## 10.6 MEASURES TO MINIMIZE BIAS

This study will be partially blinded. We will divide study participants into 2 groups. The experimental group will wear an ultraviolet sensor which will record their UV exposure. The control group will receive standard of care counseling about photoprotection from their dermatologist. The study coordinator will spend the first 10 minutes of the visit with each patient reviewing any issues related to the study, including sensor related issues. The study coordinator will remind the patient at each visit to put the sensor away from view and to not discuss any sensor related questions to the dermatologist. The dermatologist will then come in and perform a total body skin examination. Actinic keratosis will be identified, circled and photographed. The actinic keratosis will then be treated via a destruction method. Any potential skin cancers will be biopsied and sent for pathology. Cyclopyridimine butane dimer (CPD) analysis will be obtained via light curettage of the skin and mucosa. They will be sent to a lab and the data will be processed. A different physician will evaluate the results and will not have access to clinical data. This physician will remain completely blinded to the study.

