### 10.6.2 EVALUATION OF SUCCESS OF BLINDING

The study coordinator will note any failures of blinding in the randomization table.

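### The instructions to withhold assignment and to report a disclosure go to the treatment group only, so control-arm unmasking of the dermatologist who counts AKs is neither explicitly discouraged nor systematically captured

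*Combined protocol and SAP*

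**What the plan says.** Section 10.6.1 intends the treating physician to be blinded to assignment. For follow-up visits it says: "At subsequent visits subjects in the treatment group will be instructed to", followed by three items. Item (1) is to "avoid discussing their assignment with the physician". Item (2) is to keep the sensor out of the physician's sight. Item (3) is to "mention to the study coordinator if the subject of the assignment came up in conversation with the physician".

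Two other places bear on masking at the visit, and neither names an arm:

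- Section 10.6: "The study coordinator will spend the first 10 minutes of the visit with each patient reviewing any issues related to the study, including sensor related" matters. The coordinator will also "remind the patient at each visit to put the sensor away from view and to not discuss any sensor related questions to the dermatologist".
- Section 4.1: on arrival, "study personnel will pre-screen patients to ensure that the sensor is not visible to physician prior to examination".

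On detection, section 10.6.2 is a single sentence: "The study coordinator will note any failures of blinding in the randomization table".

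Section 7.1.1 has the physician identify AKs by sight and touch. Lesions are circled and photographed, and earlier photographs are reviewed to avoid double counting. Section 10.6 sends CPD results to a different, fully blinded physician. No comparable blinded second reading of the AK count is described.

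**The concern.** With two arms, a patient who says they were not given a device discloses assignment as completely as one whose sensor is seen. Of the three items in 10.6.1, only (2) depends on having a device. Items (1) and (3) apply equally to controls but are not addressed to them.

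Such a remark is foreseeable. The dermatologist gives the sun-protection advice (7.1.2), and the schedule of events (7.3.7) places UV counseling at all three visits.

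Two things are at stake. The first is the primary count, which involves judgement: a dermatologist who knows that a patient is a control might call doubtful lesions new AKs more readily, and that would favour Shade. The second is the evidence on whether blinding held. If only one arm is asked to report disclosures, a comparison of the log by arm would be hard to interpret.

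**Working it through.** **Text check.** The relevant provisions, side by side:

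| Provision | Section | Who it addresses | What it covers |
|---|---|---|---|
| Do not discuss assignment | 10.6.1 (1) | Treatment group | Assignment |
| Hide the sensor | 10.6.1 (2) | Treatment group | Sensor |
| Report if assignment came up | 10.6.1 (3) | Treatment group | Assignment |
| Coordinator's reminder | 10.6 | The patient, no arm named | Sensor and sensor questions |
| Check on arrival | 4.1 | Patients, no arm named | Sensor visibility |
| Log of blinding failures | 10.6.2 | No arm limit | Any failure; no method of finding one |

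No row asks a control to keep assignment private or to report a disclosure. The only stated route into the log is item (3).

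**Illustration of size.** The plan has no figure on this point to reproduce, and it gives neither a disclosure rate nor a counting bias. I assume that a share *u* of controls disclose, that the dermatologist's count for them rises by a fraction *x*, and that Shade has no true effect. The control mean is then inflated by *b = u × x*:

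- *u* = 20%, *x* = 10%: *b* = 2%
- *u* = 25%, *x* = 20% (or 50% and 10%): *b* = 5%
- *u* = 50%, *x* = 20%: *b* = 10%

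*Dispersion.* Section 10.5 reports power 0.81 for a 25% reduction with 50 per arm and a one-tailed t-test. Its alpha is not stated; I assume 0.05. The simulation draws on a clinical AK distribution that is not given, so 0.81 cannot be reproduced, only inverted.

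- Standard error (SE) of the relative difference at 50 per arm: 0.25/(1.645 + 0.878) = 0.0991.
- If both arms have the same SD, the coefficient of variation (CV) is 0.0991/√(2/50) = 0.495.
- If the SD scales with the mean, the control CV is 0.0991/√((1 + 0.75²)/50) = 0.56.
- CV = 1.0 is added as an assumed case of wider dispersion.

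*False positives.* With 60 per arm (120 patients, 1:1), no losses and the two-sided 0.05 test of 10.4.1, SE = CV × √(2/60) and

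P(reject) = Φ(b/SE − 1.96) + Φ(−b/SE − 1.96).

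| CV | SE | b = 2% | b = 5% | b = 10% |
|---|---|---|---|---|
| 0.495 | 0.0905 | 5.6% | 8.6% | 19.7% |
| 0.56 | 0.102 | 5.4% | 7.8% | 16.4% |
| 1.0 | 0.183 | 5.1% | 5.9% | 8.5% |

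The SD is held fixed here. If the control SD is also inflated by 1 + b, the last column becomes 18.3%, 15.3% and 8.2%. With 50 per arm and fixed SD it is 17.2%, 14.5% and 7.9%.

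**The case against.** The case on the other side has real force on four points.

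- **The reminder in 10.6 may reach controls.** It sits within time spent with every patient and names no arm, so on a broad reading controls are also told not to raise sensor questions. Telling someone to put a sensor away suggests a wearer, however, and the sentence asks nobody to keep assignment private or to report a disclosure. It narrows the gap without closing it.
- **The log is not limited to one arm.** A reader might infer that it cannot show control-arm failures. The documents do not support that: 10.6.2 covers any failure, and the coordinator could hear of one from the dermatologist or from a control unprompted. What stands is that the plan states no systematic route.
- **Controls may disclose less often.** A reader might infer that they unmask the dermatologist as easily as study patients do. Nothing in the documents shows this. Study patients carry a device that vibrates (6.1.11) and have device matters to raise; controls have nothing to show.
- **The count has safeguards.** Section 10.4 defines the lesion and requires locations and pictures, and 7.1.1 requires review of earlier photographs. These constrain the judgement but do not replace a blinded reading. Nor do the documents say that a single dermatologist does all the counting; 10.4 uses the plural.

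The disclosure rates, the over-count and its direction are all assumed. The figure near 20% joins the upper limits of two assumptions with the smallest of the standard errors, and should not be quoted as the trial's false-positive rate.

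**Conclusion.** The asymmetry is established by the text: the withhold and report instructions are addressed to one arm, and the provisions that name no arm deal only with the sensor. Followed as written, the plan leaves control-arm unmasking of the person who makes the primary count without explicit discouragement or systematic capture, and the log may under-record it relative to the study arm.

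The consequence for the result is uncertain. For assumed control-count inflation of 2-10%, the two-sided false-positive rate is about 5-6% at the low end and about 8-20% at the high end, depending on the unreported dispersion of AK counts. At low disclosure rates the effect is negligible. The documents do not show that unmasking will occur or that it would favour Shade. The change should be made because it is cheap and because disclosures not asked about at the visit cannot be reliably reconstructed later.

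**What to change.** - **10.6.1:** address items (1) and (3) to all subjects, with the same script in both arms. Keep item (2) for those who hold a device.
- **10.6.2:** after visits 2 and 3, once the AK count is recorded, have the coordinator ask every patient and the examining dermatologist whether assignment became known. Record the answers by arm and report disclosure rates by arm.
- **Do not** add a re-analysis that deletes visits where assignment came up. The primary outcome is cumulative, so removing a visit removes its AKs and mechanically lowers that patient's total. It also selects on behaviour after randomisation, and would itself bias the comparison if disclosure differs by arm.

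The cost is a few words in two sections and one short question to the patient and one to the dermatologist, at visits that already take place.

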## Software

The software consists of firmware in the device, a mobile application, and backend servers to support it. The mobile application has been designed based on user feedback to highlight issues important to people concerned about their exposure to UV light. Specifically it reports the device's estimate of the current UV Index as well as the user's cumulative exposure for the day in units of J/m^2. The software keeps a history of the exposure and allows the user to set a daily limit of UV exposure at which they will receive alerts. The backend manages each user account and stores their historical data to allow retrieval and analysis.

When the device is charged, it indicates connection by momentarily glowing green, then it indicates charging by glowing red. When the device is fully charged, and connected to power, it indicates green. Once powered up, it sends a Bluetooth (BT) signal advertises its presence. In this state it can be paired to a phone using app set to the pairing function. If the device is covered, for example by a jacket, it provides a vibration alert and a mobile phone alert periodically until it is uncovered.

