## ALARMS

In use, the device uses two methods to notify the user. (1) shade device vibration and (2) mobile phone alerts.

Notifications are triggered by the following events:

- 1) UV exposure reaches a 20 percent interval of the user's specified daily limit.
- 2) The sensor has been covered making it insensitive to UV.

Additionally, the user can trigger both alert methods by covering the proximity sensor with their finger or the vibration alert by triple tapping the battery indicator on the app's dashboard screen (Figure 2-3, first screen).

Packaging:

The device and user guide are supplied in a white 4.7 x 6.25 x 1.5 inch cardboard box labeled 'Shade.'

Labeling:

User instructions are attached as Appendix 1. The device packaging will be labeled with a sticker indicating 'For Investigational Use Only.'

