### 7.3.4 FINAL STUDY VISIT

For the final visit, a standard skin examination will be performed by a dermatologist. The scalp, face, mucous membranes, chest, back abdomen, arms, legs, genitalia, digits will be examined. Any AKs will be identified, photographed and treated as previously described. Any suspicious lesions will be biopsied. If the patient is in the study arm, the device will be collected by the study coordinator at this visit.

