### TIPS & TRICKS

Launch the app at least once a day to ensure that all the data from the sensor is synced.

Clean using only a slightly damp towel. The sensor is splash-proof, but not waterproof.

When something is covering the sensor, it vibrates three times to let you know.

A smartphone displaying the shade app interface.

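### Hiding the sensor in a pocket or purse to mask the arm can set off its covered-sensor alert, which may reveal the arm to the dermatologist counting AKs at V2 and V3

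*Combined protocol and SAP*

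**What the plan says.** Three places describe the masking step at follow-up visits.

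- Section 4.1: study personnel are to "ensure that the sensor is not visible to physician prior to examination, for example by placing it in their pocket".
- Section 10.6: the coordinator, who has the first 10 minutes of the visit with the subject, gives a reminder to "put the sensor away from view and to not discuss any sensor related questions to the dermatologist". The dermatologist then comes in.
- Section 10.6.1: treatment-group subjects are told to "place the shade sensor in a purse or pocket out of view of the physician".

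The device sections describe what happens when the sensor is covered.

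- Section 6.1.2, Software, with a jacket as the example: "it provides a vibration alert and a mobile phone alert periodically until it is uncovered".
- Section 6.1.2, Alarms, gives two notification triggers. One is "The sensor has been covered making it insensitive to UV".
- Section 6.1.11 also names covering as a cause of vibration and says the app gives similar alerts with text.
- Appendix 1, Tips & Tricks: "When something is covering the sensor, it vibrates three times to let you know".

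Under section 7.1.1 the physician identifies AKs by sight and touch. For the final visit, section 7.3.4 says "the device will be collected by the study coordinator at this visit", without saying whether this comes before or after the skin examination.

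**The concern.** Subjects know their arm and there is no sham device, so the dermatologist's blinding is the main protection for a primary endpoint that rests on judgement. The method chosen to preserve that blinding is the very condition that makes the device announce itself, and only study-arm subjects have the device.

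A dermatologist who learns the arm may call borderline lesions differently. That would create or distort a between-arm difference, and no analysis could reliably remove it afterwards.

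The plan is also poorly placed to notice. Section 10.6.1 asks subjects to report unblinding only if the assignment came up in conversation. Section 10.6.2 has the coordinator note failures, but gives no way to learn of an alert in the examination room.

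**Working it through.** The plan states no figure on this point, so the check is mainly a comparison of text.

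**1. Does the masking step cover the sensor?** Yes, if the named examples are followed. A pocket or purse covers it at least as fully as the jacket used as the example under Software. The pocket is only an example in section 4.1, and section 10.6 asks only that the sensor be out of sight, but section 10.6.1 instructs a purse or pocket directly.

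**2. Does covering trigger an alert, and does it repeat?**

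| Place | Covering triggers an alert | Repetition |
|---|---|---|
| 6.1.2 Software | Yes, device and phone | Periodic until uncovered |
| 6.1.2 Alarms | Yes, device and phone | Not stated |
| 6.1.11 | Yes, device and app | Not stated |
| Appendix 1 | Yes, device | Three vibrations; no repeat mentioned |

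All four agree on the trigger. Only the Software text supports repetition.

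**3. Can the alert fall within the examination?** The sensor is put away before the dermatologist enters. Under the Software text the alert can recur during the examination. Under the Appendix 1 text it might be over beforehand. No repeat interval, delay or loudness is given.

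**4. Does anything in the plan stop it?** No section has the sensor powered down, unpaired, silenced or kept outside the room, or the phone silenced.

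**5. Which examinations are affected?** V2 and V3, which supply the new-AK counts. V1 is not affected, because the device is handed out after the physician visit (10.6.1).

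**6. Upper limit.** Section 4.1 has 120 subjects with half in the study arm: 120 x 0.5 = 60. Two post-baseline examinations each: 60 x 2 = 120. This is a ceiling. It assumes no dropout and a charged, active sensor brought to every visit. It also includes subjects with under 15% of days used, whom section 10.4.2 drops from the primary analysis.

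**7. Illustration of the stakes only.** Suppose a share p of study-arm examinations is unblinded and a fraction u fewer lesions is counted in those. With lesions spread evenly, the spurious reduction is b = p x u. Neither p, u nor the direction comes from the documents.

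- p = 0.25, u = 0.10: b = 2.5%
- p = 0.5, u = 0.10: b = 5%
- p = 0.5, u = 0.20: b = 10%
- p = 1, u = 0.20: b = 20%

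To see what such a b does to the test, back-solve the SD/mean ratio from section 10.5 (50 per arm, 25% reduction, power 0.81). The 0.81 itself cannot be reproduced, because the AK distribution behind the simulation is not given. The standardised difference is d = (z_alpha + z_0.81) / sqrt(50/2).

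- One-sided 0.05, as in section 10.5: d = (1.645 + 0.878)/5 = 0.505; SD/mean = 0.25/0.505 = 0.495.
- Two-sided 0.05, as in section 10.4.1: d = (1.960 + 0.878)/5 = 0.568; SD/mean = 0.25/0.568 = 0.44.

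With no true effect and a two-sided 0.05 test, the chance of a significant result favouring the device is Phi(b/SE - 1.96), where SE = (SD/mean) x sqrt(2/n). The ranges cover the two SD/mean values.

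| b | 50 per arm | 60 per arm |
|---|---|---|
| 0 | 2.5% | 2.5% |
| 5% | 7.3 to 8.2% | 8.0 to 9.0% |
| 10% | 17.1 to 20.5% | 19.6 to 23.7% |

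This shows that a modest undercount would matter if it happened. It does not show that one would happen.

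**The case against.** The strongest reply is that the documents show a possible alert, not an unblinded assessor.

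- **Timing.** A reader might infer that the alarm must go off during every study-arm examination. The documents do not support that. Only one of the four descriptions mentions repetition, and no interval is given. This stands.
- **Specificity.** A reader might infer that hearing or not hearing a buzz sorts subjects into arms. It does not. Every subject in both arms must own a smartphone (5.1), so a phone alert is not specific to the study arm. Silence does not identify a control either: the battery lasts 4 days (6.1.2), and section 10.4.3 expects enough low use to define a category of 15% to 50% of days. This stands. It leaves the sensor's own vibration as the arm-specific signal, and its audibility is not stated.
- **Other safeguards.** Lesions are circled and photographed, earlier photographs are rechecked to prevent double counting, and suspicious lesions are reclassified by histology (7.1.1). Lesion locations are recorded (10.4). These limit error over whether a lesion is new or old, so blinding is not the only protection. They do not govern the initial call on a borderline lesion, and no independent blinded reading of the photographs is planned.
- **Size.** The p x u values have no source in the documents, and 120 is a ceiling. Both points stand.

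None of this removes the conflict between the masking instruction and the device description.

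**Conclusion.** The point holds as a conflict within the plan. The masking step for V2 and V3 creates the condition that, by the plan's own description, triggers device and phone alerts, and nothing prevents those alerts in the examination room. This can reveal the arm to the assessor of a subjective primary endpoint, at up to about 120 examinations.

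It does not follow that blinding will fail, or that the primary result will favour the device. The rate of unblinding and the size and direction of any bias cannot be determined from the documents, and the percentages above are illustrations only.

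Confidence is high in the textual conflict and moderate that it would unblind in practice. It should be fixed: the remedy is cheap, and biased counts cannot be reliably corrected later.

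**What to change.** 1. In sections 4.1, 10.6 and 10.6.1, replace the pocket or purse instruction. During the existing 10 minutes before the V2 and V3 examinations, the coordinator takes the sensor, or powers it down, and keeps it outside the examination room.
2. At V2, return the sensor after the examination. At V3, state in section 7.3.4 that the collection already planned happens before the examination.
3. Ask subjects in both arms to silence or switch off their phones, so that handling is the same.
4. In section 10.6.2, record any device or phone alert during an examination as a blinding failure.
5. Reconcile the Software text in section 6.1.2 with Appendix 1 on whether the covered-sensor alert repeats.

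Cost: wording changes in these sections, a brief hand-over at each of the two visits, a request about phones in both arms, and no UV recording while the subject is indoors being examined. No visit or assessment is added.
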